## **6.8      Concomitant Therapy**

Record in the CRF all concomitant therapies (e.g., medicines or nondrug interventions) used from the time the participant signs the informed consent until completion of the study, including any changes. For prescription and over-the-counter medicines, vaccines, vitamins, and herbal supplements, record the name, reason for use, dates administered, and dosing information.

Contact the Medical Monitor for any questions on concomitant or prior therapy.

Participants will abstain from taking prescription or nonprescription drugs (including vitamins and dietary or herbal supplements) within 7 days (or 14 days if the drug is a potential enzyme inducer) or 5 half-lives (whichever is longer) before the start of study intervention until completion of the Follow-up Visit, unless, in the opinion of the Investigator and Sponsor, the medication will not interfere with the study.

Paracetamol, at doses of  $\leq$  2 g/24 hours, is permitted for use across the study. Ibuprofen, at doses of  $\leq$  1,600 mg/24 hours, is permitted for use across the study. Other concomitant medication may be considered on a case-by-case basis by the Investigator in consultation with the Medical Monitor if required. Paracetamol for fever is permitted when the temperature is  $\geq$  38.0°C.

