14.5 Fever clearance time

Fever clearance time is defined as the time (in hours) from first dosing to the first measurement of temperature $< 37.5^{\circ}\text{C}$ for 2 consecutive temperature readings, plus confirmed normal temperature ($< 37.5^{\circ}\text{C}$) 24 hours after the first normal body temperature reading. Participants who are initially included on documented history of fever and who do not subsequently have a documented temperature reading of $> 37.5^{\circ}\text{C}$ at the pre-dose visit or during the 24 hours following initial dosing will not be considered for the population-level summary.

For fever clearance time, the ICEs as defined by the study protocol will be identified and handled as described in the following:

- **Intake of rescue medication:** See Section 14.1 for description of rescue medication. A composite variable strategy is applied, i.e., time to fever clearance is censored at the time of rescue medication intake. In order to qualify as ICE, the intake of rescue medication has to take place within the first 3 days after treatment initiation.
- **Intake of concomitant medications as a continuous treatment that have an impact on fever:** Filtering concomitant medications programmatically for paracetamol, acetaminophen, NSAIDs (ibuprofen, naproxen), salicylic acid, and by medical review. A composite variable strategy is applied, i.e., time to fever clearance is censored at the time of first concomitant medication intake. In order to qualify as ICE, the start date of intake of concomitant medication has to take place within the first 3 days after treatment initiation. If the fever medication was taken prior to dosing, participants will still be included for analysis. Strategies for intercurrent events will not apply.
- **Intake of prohibited medication that impacts treatment effect (e.g., drug with antimalarial activity):** Filtering concomitant medications programmatically for sulphadoxine-trimethoprim, doxycycline, quinolone antibiotics including fluoroquinolones, azithromycin, erythromycin and all other macrolides and by medical review. A composite variable strategy is applied, i.e., time to fever clearance is censored at the time of prohibited medication intake. In order to qualify as ICE, the intake of prohibited medication has to take place within the first 3 days after treatment initiation.

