- **Experience of any event that affects absorption (i.e., vomiting within the study intervention absorptive period of $2 \times \text{median } t_{\text{max}}$) or immune response (severe immunocompromised participants):** See Section 14.1 for description of events affecting absorption or immune response. A treatment policy strategy is applied, i.e., treatment effect is estimated regardless of intercurrent event.
- **Premature study discontinuation due to lack of efficacy:** See Section 14.1 for description of ICE. An on-treatment strategy is applied, i.e., time to fever clearance is censored at the day of the last available body temperature assessment. Note: If premature study discontinuation occurs after fever clearance has already been observed, then the strategy will not be applied.
- **Death due to malaria:** See Section 14.1 for description of death due to malaria. An on-treatment strategy is applied, i.e., time to fever clearance is censored at the day of the last available body temperature assessment. Note: If death occurs after fever clearance has already been observed, then the strategy will not be applied.

Median fever clearance time and 95% CIs will be estimated by use of the Kaplan-Meier method. Confidence intervals will be calculated using log-log transformation. Participants with no fever clearance or ICEs will be censored at the day of the last temperature assessment. Kaplan-Meier plots including a table with number of participants at risk and number of events will be provided. To explore whether there is an impact of dose group (Part A vs. Part B Cohort B0), age (continuous), sex, and parasite density at baseline on time to fever clearance, a Cox Proportional Hazards model will be applied.

[figure not shown]

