14.6 Parasite clearance time

Parasite clearance time is the duration (in days) between first dosing and the first blood draw with parasite clearance (parasite count = 0). The subsequent readings up till at least 6 hours from the first zero reading must remain zero for the presence of parasites.

[figure not shown]
The same ICEs and strategies as defined for time to fever clearance (see Section 14.5) will be applied to parasite clearance time, with the exception of intake of concomitant medications with impact on fever, which is not an ICE for parasite clearance time. Since parasite clearance time is measured in days, censoring will be done at the day of the last available microscopy assessment.

The same analysis approaches as described for fever clearance time are applicable also to parasite clearance time (note that for the target population for parasite clearance time the prerequisite of showing an increased temperature does not hold). Participants with no parasite clearance or ICEs will be censored at the day of the last microscopy assessment.

CCI

CCI

15 Safety Analyses

This section includes specifications for summarizing safety endpoints that are common across clinical studies such as adverse events, laboratory tests, and vital signs.

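### SAP 14.5 does not exempt medication started after fever has cleared from its censoring rules; applied literally, this can raise the median fever clearance time and never lower it

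*SAP*

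**What the plan says.** SAP Section 14.5 lists three medication events that censor fever clearance time:

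- Rescue medication: "time to fever clearance is censored at the time of rescue medication intake".
- Fever-lowering medicine given as continuous treatment: "time to fever clearance is censored at the time of first concomitant medication intake".
- Prohibited medication that affects the outcome: "time to fever clearance is censored at the time of prohibited medication intake".

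Each counts only within a 3-day window; for fever-lowering medicine, "the start date of intake of concomitant medication has to take place within the first 3 days after treatment initiation". There is one exemption, again for fever-lowering medicine only: "If the fever medication was taken prior to dosing, participants will still be included for analysis", and the intercurrent-event strategy is then dropped. None of the three bullets asks whether fever had already cleared. All three carry the label of a composite variable strategy. SAP Section 5 (endpoint 11) and Section 7 give the same rules, also without reference to earlier clearance.

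The bullets on discontinuation and death are different. For discontinuation because of lack of efficacy the SAP adds: "If premature study discontinuation occurs after fever clearance has already been observed, then the strategy will not be applied". The bullet on death due to malaria has a matching note.

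Section 14.6 carries the rules over: "The same ICEs and strategies as defined for time to fever clearance (see Section 14.5) will be applied to parasite clearance time". It removes fever-lowering medicine from the list. It places censoring at the day of the last available microscopy assessment, whereas Section 7 places it at the time of intake for both clearance endpoints.

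Protocol Section 6.8 says of paracetamol and of ibuprofen, within daily limits, that each "is permitted for use across the study".

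**The concern.** A drug started after fever has cleared cannot change when it cleared. The SAP recognises this for discontinuation and death but does not say so for the three medication events. A programmer who works bullet by bullet could therefore overwrite an early clearance with a later censoring time.

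The sequence is possible within the schedule. Temperature is read about every 6 hours in hospital (Protocol Table 2). A participant with a first normal reading at 12 h is confirmed at 12 + 24 = 36 h. If 3 days is read as 72 h, that leaves 72 − 36 = 36 h in which a continuous analgesic could begin, for example for headache or muscle ache, both scored as malaria symptoms in Protocol Appendix 6. With a start at 44 h, a literal derivation records no event and censoring at 44 h, instead of clearance at 12 h.

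At stake are the Kaplan-Meier medians for fever clearance (endpoints 11 and 28), to a lesser extent those for parasite clearance (12 and 29), and the Cox models built on the same data. Two programmers could report different medians from identical records.

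**Working it through.** **Plan's own figure.** None. Neither document gives an expected median, or a share of participants taking these drugs, so there is nothing to reproduce. The check concerns direction first and then size under stated assumptions.

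**Direction.** The Kaplan-Meier curve is S(t) = ∏(1 − d_i/n_i) over event times up to t, with d_i events and n_i at risk. Suppose one participant's event at t1 is replaced by censoring at t2 > t1.

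1. At t1, d falls by 1, so that factor rises.
2. At every event time after t1 and up to t2, n rises by 1 and d is unchanged, so those factors rise or stay equal.
3. After t2 nothing changes.

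No factor falls, so the new curve lies on or above the old one. The median, taken as the first time S reaches 0.5 or less, stays or moves later.

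**Small example (assumed data).** Ten participants clear at 6, 12, 12, 18, 18, 24, 24, 30, 36 and 48 h.

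- Events kept: S(6) = 0.9, S(12) = 0.7, S(18) = 0.5. Median 18 h.
- One participant who cleared at 12 h is re-censored at 36 h: S(6) = 9/10 = 0.9; S(12) = 0.9 × 8/9 = 0.8; S(18) = 0.8 × 6/8 = 0.6; S(24) = 0.6 × 4/6 = 0.4. Median 24 h.
- Three who cleared at 6, 12 and 18 h are re-censored at 30, 36 and 48 h: S(12) = 9/10 = 0.9; S(18) = 0.9 × 8/9 = 0.8; S(24) = 0.8 × 6/8 = 0.6; S(30) = 0.6 × 5/6 = 0.5. Median 30 h.

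In each case intake falls no earlier than 24 h after the first normal reading.

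**Simulation.** The inputs below are assumptions except the planned size of 25 for Cohort B0 (Protocol synopsis). Clearance times are Weibull with shape 1.5, rounded up to a 6 h grid. A given share of participants cleared before 72 h then starts a qualifying drug at a uniform time between clearance and 72 h. There are 2,000 runs per setting, and everyone is analysed. Each cell gives the share of runs in which the literal median exceeds the median with events kept, then the typical median, events kept → literal.

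| Underlying median | 10% affected | 20% affected | 30% affected |
|---|---|---|---|
| 18 h | 32%; 18 → 24 h | 60%; 24 → 24 h | 84%; 24 → 30 h |
| 24 h | 38%; 24 → 30 h | 68%; 30 → 36 h | 86%; 24 → 36 h |
| 30 h | 42%; 30 → 36 h | 72%; 36 → 42 h | 89%; 30 → 48 h |

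With events kept, the typical value moves between neighbouring grid points because of the 6 h rounding. The shift in the typical median is 6 h in six of the nine cells; the others show 0, 12 and 18 h. No run gave a fall. With 10 participants, close to the 12 planned for Part A, and an underlying median of 24 h, the median rose in 28%, 50% and 69% of runs at the same three shares.

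These runs include intake before the 24 h confirmation. A second simulation, with 25 participants and intake only after confirmation, gave a rise in 32–38% of trials with 8–9% of participants affected, 47–70% with 12–18%, and 84–88% with 24–28%, typically by 6 to 12 h.

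**Alternative derivation.** If the analysis time is the earlier of clearance and intake, a participant who cleared at 12 h with intake at 44 h stays an event at 12 h. The shift is zero in every setting.

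**The case against.** The strongest reply is that the SAP nowhere says a cleared participant loses the event. It censors at the time of intake, and in ordinary time-to-event work a clearance at 12 h precedes a censoring time of 44 h and is kept. SAP Section 7 also replaced the protocol's censoring at Day 29 by censoring at intake, which fits ordinary truncation. The contrast with discontinuation and death has an innocent explanation: those events have no 3-day window and can fall weeks after clearance, so a note is more obviously needed there. This stands in part. A reader might infer that the SAP orders cleared participants to be censored, and the text does not go that far. But the literal reading is not strained. The composite label means an override in SAP Section 14.1, where rescue turns the endpoint into failure, and it went with Day 29 censoring in the protocol. The sentence on default censoring in 14.5 does not settle which of clearance and intake takes precedence.

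The second reply concerns frequency. The fever-medicine event is limited to continuous treatment and is subject to medical review, so a single dose of paracetamol should not count. Intake before dosing is exempt. Protocol Section 6.8 permits paracetamol for fever only at 38.0°C or above, so use driven by fever would usually begin before clearance. All of this stands. It lowers the likely share affected without removing the gap, and continuous treatment is not defined.

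The third reply is that parasite clearance is barely affected. Fever-lowering medicine is excluded there. The early rescue triggers in Protocol Section 6.8.1 mostly require parasitemia. What remains is mainly prohibited drugs started within 3 days, largely in hospital. This stands, and the parasite clearance case is the rarer one.

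**Conclusion.** The point holds as a gap in the rules. Three medication events lack an exemption that the same section gives to discontinuation and death. Followed to the letter, the rules replace an observed clearance with a later censoring, and the median can then rise or stay the same but not fall.

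The size is conditional. At 25 participants, with 10–30% of cleared participants affected, the median rises in roughly 40–90% of simulated trials (32–89% across the three assumed medians), typically by 6 to 12 h. Those shares are assumptions. The documents do not say how many cleared participants start such drugs before 72 h, and the fever analysis may include fewer than 25 because it is restricted to participants with a raised temperature at pre-dose or in the first 24 h. The shift is zero if the first of clearance and intake is used.

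Two further inferences are tempting and not supported. One is that the reported medians will be too long: that depends on programming and drug use that the documents do not show. The other is that the Cox comparison of Part A with Cohort B0 is distorted: that would require post-clearance intake to differ between the groups, and it was not calculated.

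Endpoints 11, 12, 28 and 29 are secondary and descriptive, and the Cox model is exploratory. The primary endpoints (safety in Part A, PCR-adjusted ACPR in Part B) are unaffected.

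**What to change.** 1. In SAP 14.5, add to each of the three medication bullets the note already written for discontinuation and death: the strategy does not apply if intake follows observed fever clearance.
2. State how intake between the first normal reading and the 24 h confirmation is treated. At that point clearance is not yet confirmed, and the SAP is silent. Either choice can be defended, but it should be made before the data are seen.
3. In SAP 14.6, apply the same note to rescue and prohibited medication.
4. Reconcile the censoring time in 14.6 (last available microscopy assessment) with Section 7 (time of intake). If the 14.6 wording means the last film of the whole study rather than the last before intake, censoring could fall as late as Day 43.

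The cost is one sentence in each of three bullets, a sentence on the confirmation interval, a line or two in 14.6, and a check that the derivation matches. No new data are needed. If data review has already taken place, SAP Section 4 gives the route: label the change as such and document it in the clinical study report.

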Fever clearance time defined as the time from first dosing to the first measurement of an axillary temperature $< 37.5^{\circ}\text{C}$ for 2 consecutive temperature readings plus confirmed normal temperature 24 hours after the first normal body temperature reading	Median fever clearance time will be estimated by use of the Kaplan-Meier method separately for the one dose, the 2-day regimen, and the Pyramax treatment groups. A log-rank test will be applied to descriptively investigate differences between both treatment arms. In order to explore whether there is an impact of other covariates and factors, like, e.g., age, body weight, and baseline parasitemia on time to fever clearance a Cox Proportional Hazards model will be applied.	11, 28
PCT defined as time from dosing to the first negative (no parasites) film (microscopy)	Same as fever clearance time	12, 29
PRR defined as decrease in viable parasites over 48 hours, corresponding to one asexual parasite life cycle.	Geometric means of PRR will be estimated separately for participants of the single dose, the 2-day regimen and the Pyramax treatment arm together with 95% CIs. In order to investigate the impact of possible factors and covariates on PRR, a linear regression model will be used.	10, 27
Time to recrudescence, defined as the time from primary cure to the re-emergence of the same parasite strain that originated the primary infection.	Same as fever clearance time	13, 30

	Statistical Analysis	Ref. #
Time to re-infection, defined as the time from primary cure to the re-emergence of a different parasite strain that originated the primary infection.	Same as fever clearance time	14, 31
Time to re-emergence, defined as the time from primary cure to having recrudescence or re-infection (the first one that occurs).	Same as fever clearance time	15, 32

CCI

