#### 9.4.1.2 Efficacy Analyses Related to Secondary and **CCI** Objectives

Most of the estimands targeting the secondary objectives of this study (refer to Section 3) share the attributes of the primary estimand as described in Section 9.4.1.1. Distinct attributes of each estimand are described below for each secondary endpoint.

For the secondary efficacy endpoint fever clearance time, defined as the time from first dosing to the first measurement of an axillary temperature  $< 37.5^{\circ}\text{C}$  for 2 consecutive temperature readings plus confirmed normal temperature 24 hours after the first normal body temperature reading, the target population is defined as adult and adolescent patient with acute uncomplicated malaria due to *P. falciparum* with an increased axillary temperature ( $\geq 37.5^{\circ}\text{C}$ ). For this endpoint, the composite variable strategy that is applied to handle ICEs like intake of rescue medication and intake of concomitant medications with an impact on fever (as a continuous treatment) or intake of prohibited medication that impacts the treatment effect (e.g., drug with antimalarial activity) consists of a censoring strategy. If such ICEs are observed, those patients will be censored at Day 29. Premature study discontinuation due to lack of efficacy or malaria induced death will be handled according to an on-treatment strategy, i.e., the respective patients will be censored at the day of their last available body temperature assessment. With respect to the population-level summary, the median fever clearance time will be estimated by the Kaplan-Meier method separately for the one dose and 2-day regimen treatment groups. A log-rank test will be applied to descriptively investigate differences between both treatment arms. In order to explore whether there is an impact of other covariates and factors on time to fever clearance a Cox Proportional Hazard model will be applied. Details of the models will be described in the IAP.

The same approaches as described for fever clearance time are applicable also to PCT (note that for the target population for PCT the prerequisite of showing an increased axillary temperature does not hold).

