9.5 Software

All the analyses will be performed in SAS[®] software version 9.4 or higher.

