9.9 Definition of Duration, 'Time to' and 'Time Since' Variables

Duration will be calculated as the difference between start and end dates plus 1 (e.g., the duration of an Adverse Event (AE) = AE end date – AE start date + 1). Durations will be calculated only when both dates are available, i.e. imputed dates will not be used to compute the duration unless otherwise specified.

The time to an event will be calculated as date of event – reference date + 1 (e.g., ADT – STARTDT + 1). If time to an event is calculated in hours, then it is calculated as the difference between event and reference SAS datetimes divided by 3600 (e.g., (ADTM – STARTDTM) / 3600).

The time since an event will be calculated as:

- Date of event – reference date + 1, if the date of event is equal or greater than the reference data (e.g., days in study at onset of AE = AE start date – date of randomization + 1)
- Reference date – date of event otherwise (e.g., days since diagnosis = date of randomization – date of diagnosis)

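### Parasite clearance time is analysed in whole days with no tie method named, so its Cox dose-group hazard ratio would be pulled towards 1

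*SAP*

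**What the plan says.** SAP 14.5 fits a Cox model to fever clearance time with four terms: "To explore whether there is an impact of dose group (Part A vs. Part B Cohort B0), age (continuous), sex, and parasite density at baseline". SAP 14.6 then says: "The same analysis approaches as described for fever clearance time are applicable also to parasite clearance time". So the same model, with the same Part A versus Cohort B0 term, is fitted to parasite clearance.

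The two endpoints have different time units. For fever, "Fever clearance time is defined as the time (in hours) from first dosing to the first measurement of temperature". Under SAP 9.9, times in hours are "calculated as the difference between event and reference SAS datetimes divided by 3600". SAP 14.6 defines parasite clearance as a duration in days, and uses that unit as its reason for censoring at the day of the last film. SAP 9.9 computes any time to event that is not in hours as event date minus reference date plus 1, which is a whole number.

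Protocol 8.1 and Table 2 schedule films every 6 hours for the first 72 hours. Protocol 8.1 defines parasite clearance time without giving a unit, so the day unit is the SAP's choice.

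On software, SAP 9.5 says "All the analyses will be performed in SAS", version 9.4 or higher. I found no tie-handling method in either document.

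**The concern.** A Cox model uses the order of events. Twelve film times in the first 72 hours give a usable ordering; three or four day values give little. When many events share one value, the method for handling ties strongly affects the estimate. The Breslow approximation shrinks the hazard ratio towards 1, and the shrinkage grows with the share of the risk set that clears in each interval.

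Cohorts B1 to B3 were not enrolled, and SAP 7 drops the log-rank tests and the logistic models. In the text that can be read, the Part A versus B0 term in these two Cox models is the only modelled contrast of dose groups on efficacy. For parasite clearance, that term would be biased towards showing no dose difference, although the data to avoid this are already collected.

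**Working it through.** The plan states no hazard ratio, event count or power for these models, so there is no figure of its own to reproduce.

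**Inputs from the documents.** Part A n = 12 and Cohort B0 n = 25, so at most 37 events. Films every 6 hours to 72 hours, so 72/6 = 12 film times. In 24-hour blocks, 72/24 = 3 values.

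**Assumptions, not in the documents.** True hazard ratio 2.0 (B0 versus Part A); Weibull clearance times; Part A median 12 to 36 h; shape 1 or 2; administrative cut at 72 h; Breslow as the default.

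**Hand check.** Take exponential times (shape 1). Let q be the probability that a Part A participant who is still positive stays positive through one interval: q = 0.5^(interval/median). With a hazard ratio of 2, the B0 probability is q². The Breslow limit is the ratio of the interval clearance probabilities, (1 − q²)/(1 − q) = 1 + q.

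- Median 24 h, 24-hour interval: q = 0.50, limit 1.50.
- Median 12 h, 24-hour interval: q = 0.25, limit 1.25.
- Median 36 h, 24-hour interval: q = 0.63, limit 1.63.
- Median 24 h, 6-hour interval: q = 0.84, limit 1.84.

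Large-sample simulation gives 1.49, 1.25, 1.63 and 1.84 for the same settings. A complementary log-log model instead estimates ln(q²)/ln(q) = 2, whatever the interval width.

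**At the trial's size.** Median estimated hazard ratio, single-covariate model, 12 versus 25, 1,500 runs per row, true value 2.0:

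| Part A median, shape | 24-h blocks: Breslow | 24-h blocks: Efron | 6-h grid: Breslow | 6-h grid: Efron |
|---|---|---|---|---|
| 12 h, 1 | 1.25 | 1.66 | 1.72 | 1.97 |
| 18 h, 1 | 1.39 | 1.78 | 1.79 | 1.97 |
| 24 h, 1 | 1.51 | 1.85 | 1.88 | 2.03 |
| 36 h, 1 | 1.63 | 1.92 | 1.92 | 2.02 |
| 12 h, 2 | 1.09 | 1.33 | 1.58 | 1.86 |
| 18 h, 2 | 1.24 | 1.51 | 1.67 | 1.90 |
| 24 h, 2 | 1.35 | 1.67 | 1.75 | 1.96 |
| 36 h, 2 | 1.49 | 1.78 | 1.83 | 1.98 |

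The 24-hour blocks average 1.6 to 3.0 distinct event times, against 4.6 to 10.2 on the six-hour grid.

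**Calendar days.** SAP 9.9 counts dates, not 24-hour blocks from dosing. Separate runs on calendar days (medians 18 to 36 h, shapes 1 to 4) gave Breslow 1.23 to 1.72 and Efron 1.46 to 2.00, so the pattern is the same.

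**Film intervals.** In further runs (medians 18 to 36 h, shapes 1 to 4), whole days gave Breslow 1.24 to 1.49 and Efron 1.44 to 1.82. The complementary log-log model on six-hour intervals gave 2.09 to 2.14.

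**Actual clock times.** With six-hourly readings jittered by up to 30 minutes (the SAP 9.4 window), Breslow gave 1.89 to 2.05 over the settings in the table.

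**Size against noise.** On the log scale the Breslow shift runs from ln 2.00 − ln 1.63 = 0.693 − 0.489 = 0.20 to ln 2.00 − ln 1.09 = 0.693 − 0.086 = 0.61. The SD of the log hazard ratio is about 0.4 on the six-hour grid, so the shift is about 0.5 to 1.5 SD. Even without bias, an estimate of 2.0 would carry a 95% interval of about exp(0.693 ± 1.96 × 0.4), that is 0.9 to 4.4.

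**The case against.** The strongest reply is that nothing rests on this hazard ratio. The model is exploratory. Part A and B0 were not randomised against each other and differ by design in age range and parasitaemia ceiling (50,000 versus 150,000 per µL). SAP 7 says the protocol's comparison of treatment groups will not be conducted. All of that stands, and it keeps the point minor. It does not justify reporting an estimate with a known, avoidable bias.

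It is also fair that the size rests on assumed medians, shapes and a true ratio of 2.0, and that the Breslow default is not in the documents. A programmer might choose Efron. The Efron columns show that on whole days this usually recovers only part of the loss, because much of it comes from the day unit.

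One could read the day unit as allowing fractional days from datetimes. SAP 9.9 gives the datetime rule only for times in hours, and SAP 14.6 censors by day because of its unit. Whole days is the natural reading.

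A reader might infer that fever clearance suffers equally, since temperatures are also taken mostly six-hourly in hospital. The documents do not support this. SAP 14.5 and 9.9 put fever times on actual datetimes, so ties are few and the attenuation nearly vanishes. It would return only if nominal times were programmed, which SAP 9.9 does not say.

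**Conclusion.** The point holds for parasite clearance time. As SAP 14.6 and 9.9 are written, up to 37 events collapse onto a few day values and the tie method is left open. Under Breslow ties, a true hazard ratio of 2.0 would be estimated at about 1.1 to 1.6. Efron on whole days gives about 1.3 to 1.9. Both ranges rest on Part A medians of 12 to 36 h, Weibull shapes 1 to 2, 24-hour blocks and clearance judged within 72 h. The bias is towards no dose effect. With an exploratory, non-randomised contrast this imprecise, it is worth correcting but changes no decision in the plan.

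A reader might also infer that leaving body weight out of the Cox model breaches the protocol. It does not. Protocol Table 9 offers covariates only as examples, "like, e.g., age, body weight, and baseline parasitemia on time to fever clearance a Cox Proportional Hazards model will be applied", and Protocol 9.4.1.2 adds: "Details of the models will be described in the IAP". The SAP was free to choose age, sex and parasite density. At most, a sentence giving the reason for omitting weight would help.

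**What to change.** In SAP 14.6, derive parasite clearance time in hours from actual datetimes, as SAP 9.9 already provides for fever clearance. State censoring at the time, not the day, of the last film. Then take one of two routes:

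- fit the Cox model with TIES=EFRON or TIES=EXACT; or
- fit a discrete-time complementary log-log model on the six-hour film intervals. With at most 37 events, the baseline may need pooled intervals or a simple smooth form.

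Name the same tie option in SAP 14.5 for consistency; it will change little there. Record the change of unit in the SAP modification history.

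The cost is slight reprogramming. The films are already scheduled, and checking the 30-minute windows in SAP 9.4 already requires their actual times. No extra data or participants are needed.
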